#### *Specific renal endpoints*

The frequency of patients with  $\geq 2$  fold increase of creatinine from baseline will be presented.

For non-Japanese adult patients, the glomerular filtration rate will be estimated according to the MDRD formula, consistent with the recommendation of the US NIH, NIDDK (National Institute of Diabetes and Digestive and Kidney Diseases of the ~~the~~ National Institute of Health) as of October 2012. In the formula for non-Japanese, adult patients the factor of 175 accounts for IDMS traceable determination of creatinine:

- MDRD formula for adult, non-Japanese patients

$$\text{eGFR (mL/min/1.73m}^2\text{)} = 175 \times (\text{creatinine } (\mu\text{mol/L}) / 88.4)^{-1.154} \times \text{age}^{-0.203} \\ \times (0.742 \text{ if female}) \times (1.212 \text{ if black})$$

- eGFR formula for adult Japanese patients

$$\text{eGFR (mL/min/1.73m}^2\text{)} = 194 \times \text{creatinine (mg/dL)}^{-1.094} \times \text{age}^{-0.287} \times (0.739 \text{ if female})$$

A patient will be considered to be of Japanese origin if the patient was screened at a site located in Japan and is of Asian Race.

Calculation of age will be done by:

- $\text{age} = (\text{laboratory assessment date} - \text{date of birth} + 1) / 365.25$ .

To support analysis of renal function, eGFR throughout the trial will be categorised according to the following MDRD staging and a shift table will be provided based on standardized observed values. (This shift table will be provided based on a treatment emergent approach and independent of treatment.)

Table 7.8.2: 1 MDRD staging

Stage	eGFR [mL/min/1.73m  ]	Description
1	>=90	Normal renal function
2	60 to <90	Mild renal function impairment
3a	45 to <60	Moderate renal function impairment 3a
3b	30 to <45	Moderate renal function impairment 3b
4	15 to <30	Severe renal function impairment
5	<15	Kidney failure

Only the albumine / creatinine ratio will be analysed as for urinary albumine and creatinine no normalised values can be derived.

The UACR will be determined (by the laboratory) based on urinary albumine and urinary creatinine measures from the same urine sample as:

$$\begin{aligned} \text{UACR } (\mu\text{g}/\text{mg crea}) &= \text{urinary albumine (mg/dL)} / \text{urinary creatinine (g/dL)} \\ &= \text{urinary albumine (mg/dL)} / (8.84 \times \text{urinary creatinine (mmol/dL)}) \end{aligned}$$

For descriptive analyses log10 transformed UACR values will be derived and their change from baseline (as difference between log10 transformed values) will be determined.

A shift table will be provided based on standardized observed values. (This shift table will be provided based on a treatment emergent approach and independent of treatment.)

Table 7.8.2: 2 UACR categorisation

Stage	UACR	Description	Label for displays
1	<30	Normal UACR	<30 mg/g (normal)
2	>=30 to <=300	Microalbuminuria	>=30 to <=300 mg/g (elevated)
3	>300	Macroalbuminuria	>300 mg/g (high)

In addition, a shift table based on the KDIGO categories will be provided from baseline to last value on treatment:

Table 7.8.2: 3 Prognosis of chronic kidney disease by GFR and albuminuria category

		UACR (mg/gcrea)		
		<30	>=30 to <=300	>300
eGFR (MDRD) [mL/min/1.73m  ]	>=90	low risk	moderately increased risk	high risk
	60 to <90	low risk	moderately increased risk	high risk
	45 to <60	moderately increased risk	high risk	very high risk
	30 to <45	high risk	very high risk	very high risk
	15 to <30	very high risk	very high risk	very high risk
	<15	very high risk	very high risk	very high risk

*Clinically significant abnormal laboratory values*

The definition of clinically significant abnormal laboratory safety values will follow the BI standard rules (5) except for fasting plasma glucose. A fasting plasma glucose value less than 54 mg/dL (<3.0 mmol/L) will be considered a clinically relevant decrease, a clinically relevant increase is not defined for this trial.

*Investigation of amylase and lipase*

Following analyses will be performed for amylase and lipase:

- Descriptive statistics for baseline, last value on-treatment and follow-up value
- Descriptive statistics for values over time (on-treatment including values before and after antidiabetic rescue therapy)
- Shift tables for baseline, last value on treatment and maximum value on treatment with categorisation of <LLN, LLN to ULN, ULN to <=3ULN, >=3\*ULN and for every week

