#### A) Previous Vascular Disease:

- Myocardial infarction (> 6 weeks prior to informed consent)

Proprietary confidential information.

© 2019 Boehringer Ingelheim International GmbH or one or more of its affiliated companies. All rights reserved.

This document may not - in full or in part - be passed on, reproduced, published or otherwise used without prior written permission.

- Documented coronary artery disease ( $\geq 50\%$  luminal diameter narrowing of left main coronary artery or  $\geq 50\%$  in at least two major coronary arteries in angiogram) Note: CT or MRI detection of this will not suffice for inclusion; only invasive angiography. The left main coronary artery is often abbreviated to LCA or LCMA. As this is a very important artery that is branched to other major arteries it suffices to have a  $\geq 50\%$  stenosis in this artery (any segment) for inclusion. If there are no stenosis in this artery patient could be included if patient has a  $\geq 50\%$  stenosis in two, or more, of the other major coronary arteries (any segment): LAD (Left Anterior Descending; also called AIB = Anterior interventricular branch), CX (= art. Circumflex, also called CB=Circumflex branch) or RCA (right coronary artery).
- Percutaneous Coronary Intervention (PCI) > 6 weeks prior informed consent
- Coronary Artery By-pass Grafting (CABG) > 4 years prior to informed consent or with recurrent angina following surgery
- Ischemic or hemorrhagic stroke (> 3 months prior to informed consent)
- Peripheral occlusive arterial disease (previous limb bypass surgery, stenting or percutaneous transluminal angioplasty; previous limb or foot amputation due to circulatory insufficiency, angiographic or ultrasound detected significant vessel stenosis (> 50%) of major limb arteries (common iliac artery, internal iliac artery, external iliac artery, femoral artery, popliteal artery), history of intermittent claudication, with an ankle: arm blood pressure ratio < 0.90 on at least one side).

B) Evidence of vascular related end-organ damage:

- Moderately impaired renal function (as defined by modified diet of renal disease (MDRD) formula) with estimated glomerular filtration rate [eGFRF]) 30-59 mL/min/1.73 m^2
- Random spot urinary albumin: creatinine ratio  $\geq 30$   $\mu\text{g}/\text{mg}$  ( $\geq 3.4$  mg/mmol) in two of three unrelated specimens in previous 12 months prior Visit 1a

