#### 5.2.3.3 Urinalysis

- Albumin, Creatinine (spot urine – quantitative measurement)
- Protein
- Ketone
- Leucocytes

Visit 1a safety laboratory only includes ALT (SGPT), AST (SGOT), alkaline phosphatase, serum creatinine, urine analysis and urine albumin and creatinine, in addition to HbA1c and does not need to be collected in fasted state.

Exact date and time of blood sampling should be recorded on the central laboratory requisition form.

Albumin/creatinine ratio will be calculated at the central lab.

Pregnancy testing (urine dipstick method) will be performed in female patients of child-bearing potential according to the [Flow Chart](#). Testing will be performed locally, using pregnancy test kits provided by the central laboratory.

Immediately after the result of a pregnancy test is known, the pregnancy test kit will be discarded at the site. The result of the test must therefore be documented in the source documents available at site for future verification by the on-site monitor.

A negative pregnancy test result is required at Visit 2 for all female patients of childbearing potential to remain eligible for entry into the treatment phase of the trial.

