#### 5.2.2.2 Secondary diabetes related endpoints

Secondary diabetes related endpoints include change from baseline to Final Visit in the following laboratory parameters:

- HbA1c
- Fasting plasma glucose
- Total cholesterol
- LDL cholesterol
- HDL cholesterol
- Triglycerides
- Creatinine
- eGFR (MDRD formula)
- Urinary albumin

In addition any transition in albuminuria classes will be investigated by using UACR. Please refer to [Table 7.8.2: 2](#) for the definition of classes.

For these endpoints, the final visit value refers to the last value obtained on treatment. Parameter-specific on-treatment phases are defined according to [Section 6.7.2](#). The intake of rescue medication is considered as described in [Section 5.2.1](#).

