### **6.8.2 Date of event**

For composite outcomes, e.g. time to 4P-MACE, 3P-MACE and time to the first occurrence of any of the components of the composite endpoint of all CEC confirmed adjudicated events, the earliest onset date of the corresponding components will be used. For fatal MI and fatal stroke the onset date of the event is used while for other CV deaths, the date of death is used.

The date determined by the adjudication committee will be used; this can be different from the investigator reported date.

For the endpoints of time to CV death, time to all-cause mortality and time to non CV death the respective death date will be used.

The time to the first silent MI is determined by the onset date of the adverse event defined as silent MI by the investigator.

For events with multiple episodes, such as hypoglycaemia, the onset date of the first episode will be used. The same applies to time-to-AE analysis.

For time to rescue medication, the first intake of rescue medication (or respectively increase in background medication dose) will be used.

The time to first occurrence of endpoints based on laboratory data, e.g. 'time to first new onset of macroalbuminuria' is determined by the date of the first laboratory measurement, in this example UACR measurement, that fulfils this condition.

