#### Treatment-emergent evaluation

Patients with a baseline measurement and at least one on-treatment measurement will be included for analysis over time. Only values obtained until last permanent treatment stop will be considered. The assignment of values to be on-treatment is defined in [Table 6.7.2: 1](#).

In general, for the evaluation of HbA1c and FPG, for patients receiving rescue therapy all on-treatment efficacy measurement after the start of rescue therapy will not be used for analysis and hence set to missing (OC, LOCF). If a patient receives rescue therapy before the first available on-treatment measurement, this patient will not be included in the analysis, except for HbA1c LOCF analysis.

For total cholesterol, HDL cholesterol, LDL cholesterol, triglycerides, creatinine, urinary albumin, UACR, eGFR and weight values before and after rescue therapy intake will be considered (OC-ROC, LOCF-ROC).

In addition, analyses following the OC concept will be performed.

For the following parameters, only values obtained in the fasted state will be used for analyses: FPG, total cholesterol, HDL cholesterol, LDL cholesterol, triglycerides.

For UACR log10 transformed data will be used within the ANCOVA or respectively MMRM model, the results will be back-transformed to the original scale.

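### SAP 7.8.2: the second line of the UACR formula has 8.84 on the wrong side and gives values 78-fold below the first line

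*SAP*

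**What the plan says.** SAP 7.8.2, under Specific renal endpoints, says that the laboratory determines UACR, in µg per mg creatinine, from albumin and creatinine in the same urine sample. It then gives two expressions joined by an equals sign (quotes keep the typesetting code of the formulas):

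- Line 1: "urinary albumine (mg/dL)} / \text{urinary creatinine (g/dL", that is, albumin in mg/dL over creatinine in g/dL.
- Line 2: the same albumin divided by a bracket that contains "8.84 \times \text{urinary creatinine (mmol/dL", that is, 8.84 times creatinine in mmol/dL.

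Two other places fix the conversion between mass and molar creatinine:

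- The MDRD equation under the same heading turns µmol/L into mg/dL by dividing by 88.4: "creatinine } (\mu\text{mol/L}) / 88.4)^{-1.154".
- Protocol 3.3.2, risk category B, sets the albumin-to-creatinine entry threshold at 30 µg/mg and gives its molar equivalent as 3.4 "mg/mmol) in two of three unrelated specimens in previous 12 months prior Visit 1a".

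On who does the calculation, Protocol 5.2.3.3 states: "Albumin/creatinine ratio will be calculated at the central lab".

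UACR is then used in two ways. Some outputs are class-based. SAP 5.2.2.2 says "In addition any transition in albuminuria classes will be investigated by using UACR", Tables 7.8.2: 2 and 7.8.2: 3 cut UACR at 30 and 300 mg/g, and SAP 6.8.2 gives "time to first new onset of macroalbuminuria" as an example of a laboratory-based event. Others are on the log scale: "For UACR log10 transformed data will be used within the ANCOVA or respectively MMRM model" (SAP 7.5.2.2.1).

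**The concern.** Line 2 is offered as equivalent to line 1, but the units do not allow it. The two agree only if 1 mmol of creatinine weighs 8.84 g. The conversions elsewhere in the documents imply the inverse: 1 g of creatinine is 8.84 mmol.

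Line 2 is the form that someone holding urinary creatinine in molar units would reach for when checking or re-deriving the ratio. Because the albuminuria classes use fixed cut-offs, a multiplicative error in UACR moves patients between classes. The exposed outputs are the albuminuria transitions, the UACR and KDIGO shift tables, and any event defined by crossing the macroalbuminuria limit.

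**Working it through.** **Inputs**

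- Creatinine conversion: 88.4 µmol/L per mg/dL (SAP 7.8.2, MDRD equation).
- Entry threshold: 30 µg/mg, equated with 3.4 mg/mmol (Protocol 3.3.2, category B).
- Class limits: 30 and 300 mg/g (SAP Table 7.8.2: 2). Note that 1 mg/g = 1 µg/mg.

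**Step 1: check line 1.** Albumin (mg/dL) / creatinine (g/dL) has units mg/g, which is µg/mg. Line 1 is correct.

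**Step 2: conversion implied by the SAP.** 1 mg/dL = 88.4 µmol/L. Multiplying by 1,000 gives 1 g/dL = 88.4 mmol/L, and dividing by 10 gives 1 g/dL = 8.84 mmol/dL. So creatinine (g/dL) = creatinine (mmol/dL) / 8.84.

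**Step 3: cross-check against the protocol.** 30 / 3.4 = 8.82 mmol per g. Allowing for rounding of 3.4 (3.35 to 3.45), the range is 30/3.45 = 8.70 to 30/3.35 = 8.96, which contains 8.84. In the other direction, 3.4 × 8.84 = 30.06, which agrees with 30. Line 2 would turn 3.4 mg/mmol into 3.4 / 8.84 = 0.385 µg/mg.

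**Step 4: ratio of the two lines.** Let A be albumin (mg/dL) and C creatinine (g/dL), so that molar creatinine is 8.84 × C mmol/dL.

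- Line 1 = A / C
- Line 2 as printed = A / (8.84 × 8.84 × C) = A / (78.15 × C)
- Line 1 / line 2 = 8.84² = 78.15 for every sample; log10(78.15) = 1.893

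**Step 5: samples with creatinine 0.1 g/dL (0.884 mmol/dL)**

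| Albumin (mg/dL) | Line 1 | Line 2 as printed | 8.84 × A / creatinine (mmol/dL) |
|---|---|---|---|
| 3 | 30.0 | 0.384 | 30.0 |
| 30 | 300.0 | 3.84 | 300.0 |

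The equality stated in the SAP (ratio 1) is not reproduced. With 8.84 in the numerator it is.

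**Step 6: could a wrong unit label explain it?** For albumin 3 mg/dL and creatinine 0.1 g/dL, line 1 gives 30. Reading the creatinine in line 2 in other molar units gives 0.0384 (mmol/L), 0.0000384 (µmol/L), 38.4 (mol/L) or 384 (mol/dL). None gives 30.

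**Step 7: effect on the classes if line 2 were applied.** To read 30, the true UACR would have to be 30 × 78.15 = about 2,344 mg/g. To exceed 300, it would have to be above 300 × 78.15 = about 23,444 mg/g. Nearly all patients would be classed as normal.

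**Step 8: effect on log10 changes.** A fall from 150 to 45 mg/g is log10(45/150) = −0.523. With both values divided by 78.15 (1.919 and 0.576) the change is again −0.523. A factor applied throughout cancels in changes from baseline and in treatment ratios.

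**The case against.** The arithmetic is not in dispute. The case on the other side is that the error has little consequence.

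- **The laboratory calculates the ratio.** Both documents say so. The SAP text describes how the value arises and does not instruct programmers to recompute it. This stands: no document shows line 2 in use.
- **Timing.** SAP 6.7 puts randomisation between December 2010 and December 2012, and the first signed analysis plan is dated 22 January 2014. The laboratory's method for baseline samples therefore cannot have come from the plan. This also stands, and it leaves sponsor-side recomputation or checking as the main route to harm.
- **The correct definition is there.** Line 1 comes first, and the output units and class labels are on its scale. A table showing almost everyone as normal would be conspicuous in a trial that admits patients on a ratio of 30 µg/mg or more. This makes an undetected error less likely, but it does not make line 2 right.
- **The outputs are exploratory or descriptive.** This is correct. In addition, new-onset macroalbuminuria appears in SAP 6.8.2 only as an example, and the available text does not define it as an endpoint.
- **The formula was read from a PDF.** A displaced bracket cannot be wholly excluded. However, the printed brackets are explicit, and exponents elsewhere in the section survived.

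These points bear on how likely harm is. They do not rescue the equality, which stands in the current SAP as part of the definition of UACR.

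**Conclusion.** The concern holds. Line 2 of the UACR definition is wrong as written: 8.84 multiplies molar creatinine in the denominator where it should divide it, so line 2 is 78.1-fold below line 1 (−1.89 on the log10 scale) for every sample. The result rests only on the SAP's own 88.4 conversion and is confirmed by the protocol's 30 µg/mg and 3.4 mg/mmol pair. No outside figure is needed.

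The consequence is conditional. If line 2 were applied, the class-based albuminuria outputs would be invalid. Log10 changes and treatment ratios would be unaffected provided the factor was applied throughout. Eligibility and the primary and key secondary endpoints do not depend on the formula. The documents do not show that any trial data are affected. The correction should be made because the error is certain, the class-based outputs are sensitive to it, and the remedy is nearly free.

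**What to change.** In SAP 7.8.2, replace line 2 with UACR (µg/mg) = 8.84 × urinary albumin (mg/dL) / urinary creatinine (mmol/dL), or delete it and keep line 1 alone.

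Before database lock, obtain written confirmation from the central laboratory of the formula and units behind the reported ratio. Confirm also that no analysis program derives UACR from line 2.

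The cost is a one-line SAP correction and one query each to the laboratory and programming. It needs no new data and changes nothing in the confirmatory analyses.

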### **7.8.3 Vital signs**

In-clinic pulse rate, SBP and DBP will be summarised by treatment group per week and as change from baseline to each week using descriptive statistics based on the treated set.

### **7.8.4 ECG**

Clinically relevant abnormal findings will be reported as AEs or respectively as baseline conditions.

Any findings resulting in an assessment of silent MIs or adjudicated confirmed outcome events will be analysed as described in [Sections 7.4](#) and [7.5](#). AE analysis will take place as planned in [Section 7.8.1](#).

Heart rate will be summarised by treatment group per week and as change from baseline to each week using descriptive statistics based on the treated set.

### **7.8.5 Others**

#### **Waist circumference**

Simple descriptive statistics over time is planned on the TS, based on observed values (without imputation).

#### **Modified Rankin scale**

The endpoint of occurrence of or time to first disabling or fatal stroke will be based on the MRS assessment. In case of a missing assessment, the grade will be set to 5, if the patient has not died, otherwise to grade 6. If an MRS assessment is available for a stroke, but has not been confirmed by the adjudication committee, this assessment will not be used for the endpoint of time and occurrence of first disabling or fatal stroke.

As a supporting analysis missing MRS assessments will not be imputed.

#### **Titration**

Overviews on titration including investigator's reasons will be presented.

## 10. HISTORY TABLE

Table 10: 1 History table

Version	Date (DD-Mmm-YY)	Author	Sections changed	Brief description of change
First	22-Jan-14		None	This is the draft TSAP without any modification
Second final	11-Aug-16		Refer to Section 4	Refer to Section 4
Revised	16-March-18		Refer to Section 4	Refer to Section 4, Reference for ICH E9 added

